## **9.2 Test and Observation Items and Time Points**

### **9.2.1 Items Related to Demographic Characteristics**

#### **9.2.1.1 Medical History/Demographic Characteristics**

The investigator (or subinvestigator) will identify the following subject demographic characteristics at screening (Days –30 to –2) and record the results in the CRF.

- (1) Sex
- (2) Date of birth (in AD)
- (3) Height
- (4) Body weight
- (5) Race
- (6) Medical history/complications
- (7) History of allergy (including drug allergies)
- (8) Drinking status
- (9) Smoking status

#### **9.2.1.2 Inclusion/Exclusion Criteria**

The investigator (or subinvestigator) will confirm that each subject meets the inclusion or exclusion criteria at screening (Days –30 to –2), Day –1 (hospitalization), and Day 1 (pre-dose) and record the result in the CRF.

#### **9.2.1.3 Serological Test**

A serological test (hepatitis B surface antigen, serological test for syphilis, hepatitis C virus antibody, and HIV antigen/antibody) will be performed at screening (Days –30 to –2). The investigator (or subinvestigator) will record the results in the CRF for fulfillment of the inclusion and exclusion criteria.

#### **9.2.1.4 Drug and Alcohol Abuse Screening**

At screening (Days –30 to –2) and Day –1 (hospitalization), the subjects will undergo the urine drug test (phencycline, cocaine, barbiturates, tetrahydrocannabinol, benzodiazepines, amphetamine/methamphetamine, and morphine) and urine alcohol test. The investigator (or subinvestigator) will record the results in the CRF for fulfillment of the inclusion and exclusion criteria.

### 9.2.1.5 Height, Body Weight, and BMI

The subjects' height and body weight will be measured, and the BMI will be calculated at the time points shown in the table below. The investigator (or subinvestigator) will record the height and body weight in the CRF. On Day –1, the BMI will be calculated based on the height at screening and body weight on Day –1.

Part 1 (single-dose study)	Part 2 (multiple-dose study)

Screening: Height, body weight, BMI

Day –1 (hospitalization): Body weight, BMI

End-of-study assessment: Body weight

	

Screening: Height, body weight, BMI

Day –1 (hospitalization): Body weight, BMI

End-of-study assessment: Body weight

BMI formula:

BMI = Body weight (kg)/height (m) (rounded to one decimal place)

### 9.2.2 Concomitant Medications

The investigator (or subinvestigator) will confirm whether each subject has used any medications (including commercially available drugs) other than the study drug, between 7 days before the start of study drug administration and completion of the end-of-study assessment. If any, the investigator (or subinvestigator) will record the drug name, dose, unit, route, frequency, duration, and reason for administration in the CRF.

### 9.2.3 Treatment Compliance

The investigator (or subinvestigator) will record the dose, date, and time of administration of the investigational drug or comparator in the CRF.

### 9.2.4 Safety Assessments

An acceptable time range for each assessment will be specified in a separate document.

#### 9.2.4.1 Physical Examination

The investigator (or subinvestigator) will assess the subjects for any abnormal findings and AEs at the time points shown in the table below.

Part 1 (single-dose study)	Part 2 (multiple-dose study)

Screening

Day –1 (hospitalization)

Day 1: Pre-dose and 1, 3, 6, and 12 hours post-dose

Day 2: Before breakfast

Day 3: Before breakfast

End-of-study assessment

	

Screening

Day –1 (hospitalization)

Day 1 to Day X*1: Before breakfast (pre-dose) and 1, 3, 6, and 12*2 hours post-dose

Day X*1 + 1: Before breakfast

Day X*1 + 2: Before breakfast

End-of-study assessment

\*1: X = duration (in the case of a 5-day administration, X = 5)

\*: For twice daily administration, the examination after 12 hours will be done before administration.

#### 9.2.4.2 Laboratory Tests

The following laboratory tests will be performed at the time points shown in the table below. If blood sampling and a 12-lead ECG or vital sign measurement are scheduled at the same time point, blood will be drawn after the 12-lead ECG or vital sign (except for body temperature) measurement. The investigator (or subinvestigator) will record the results in the CRF.

The approximate blood volume per sampling is 2 mL for 1), 6 mL for 2), and 1.8 mL for 3), described below.

- 1) Hematology: Hemoglobin, hematocrit, RBC count, WBC count, platelet count, MCH, MCHC, MCV, differential white blood cell count
- 2) Biochemistry: Na, K, Cl, Ca, inorganic phosphorous, urea nitrogen, creatinine, uric acid, total bilirubin, direct bilirubin, ALT, AST, γ-GTP, ALP, LDH, CK, amylase, total cholesterol, triglyceride, LDL-C, HDL-C, total protein, albumin, glucose
- 3) Coagulation test: Prothrombin time, activated partial thromboplastin time
- 4) Urinalysis: Sediment, qualitative analysis (pH, specific gravity, protein, glucose, occult blood, urobilinogen, bilirubin, ketone body)

Part 1 (single-dose study)	Part 2 (multiple-dose study)

• Screening

• Day –1 (hospitalization)*1

• Day 2: Before breakfast

• End-of-study assessment

	

• Screening

• Day –1 (hospitalization)*1

• Day X*2: Before breakfast (pre-dose)

• End-of-study assessment

\* On Day –1 (hospitalization), the assessment will be performed based on results that can be confirmed within the same day.

\* When X = 5 (5-day administration), Days 3 and 6.

When X = 9 (9-day administration), Days 3, 7, and 10.

When X = 14 (14-day administration), Days 3, 7, 11, and 15.

The sponsor will calculate the estimated glomerular filtration rate (eGFR) from creatinine, using the most recent body weight.

#### 9.2.4.3 Vital Signs

The systolic and diastolic blood pressure, pulse rate, and axillary body temperature (in Celsius; rounded to one decimal place) of each subject will be measured at the time points shown in the table below. The investigator (or subinvestigator) will record the date, time, and results of measurement in the CRF.

Systolic and diastolic blood pressure will be measured after at least a 5-minute rest in a lying position. One measurement will be taken for each time point. The measurements will be taken in the same arm throughout the study period, in principle.

If blood sampling and a 12-lead ECG or vital sign (except for body temperature)

measurement are scheduled at the same time point, blood will be drawn after the 12-lead ECG or vital sign (except for body temperature) measurement.

Part 1 (single-dose study)	Part 2 (multiple-dose study)

Screening

Day -1 (hospitalization)

Day 1: Pre-dose and 1, 3, 6, and 12 hours post-dose

Day 2: Before breakfast

Day 3: Before breakfast

End-of-study assessment

	

Screening

Day -1 (hospitalization)

Day 1 to Day X: Before breakfast (pre-dose) and 1, 3, 6, and 12 hours post-dose

Day X + 1: Before breakfast

Day X + 2: Before breakfast

End-of-study assessment

\*: X = duration (in the case of a 5-day administration, X = 5)

\*: For twice daily administration, the examination after 12 hours will be done before administration.

#### 9.2.4.4 12-lead ECG

After at least a 5-minute rest in a lying position, a 12-lead ECG will be recorded at the time points shown in the table below. The investigator (or subinvestigator) will record the date and time of measurement, heart rate, QTcF, PR interval, QT interval, RR interval, QRS interval, and findings in the CRF.

If blood sampling and a 12-lead ECG or vital sign (except for body temperature) measurement are scheduled at the same time point, blood will be drawn after the 12-lead ECG or vital sign (except for body temperature) measurement.

Part 1 (single-dose study)	Part 2 (multiple-dose study)

Screening

Day -1 (hospitalization)

Day 1: Pre-dose and 1, 3, 6, and 12 hours post-dose

Day 2: Before breakfast

Day 3: Before breakfast

End-of-study assessment

	

Screening

Day -1 (hospitalization)

Day 1 to Day X: Before breakfast (pre-dose) and 1, 3, 6, and 12 hours post-dose

Day X + 1: Before breakfast

Day X + 2: Before breakfast

End-of-study assessment

\*: X = duration (in the case of a 5-day administration, X = 5)

\*: For twice daily administration, the examination after 12 hours will be done before administration.

#### 9.2.4.5 Sensory Tests

The investigator (or subinvestigator) will check whether the subject has any symptoms of numbness, dizziness or vibratory sensation at the time points shown in the table below, evaluating numbness and dizziness by interview and vibratory sensation with a tuning fork, and record the results in the CRF.

- Numbness: Present/absent (If present → Severity)
- Dizziness: Present/absent (If present → Severity)
- Vibratory sensation (left and right): Seconds (measure of time that vibration is felt when the handle of a vibrating 128 Hz tuning fork is put against the outer ankle)

If present, the severity will be graded on the following 3-point scale.

[Severity]

- 1) Mild: The event does not interfere with activities of daily living.
- 2) Moderate: The event interferes to some extent with activities of daily living.
- 3) Severe: The event interferes significantly with activities of daily living.

Part 2 (multiple-dose study)
• Day -1 (hospitalization)
• Day X* + 1: Before breakfast

\*X = duration (in the case of a 5-day administration, X = 5)

#### 9.2.4.6 Adverse Events

An adverse event (AE) is any untoward medical occurrence or unintended sign (including an abnormal laboratory finding), symptoms, and disease in a patient or subject who is administered a pharmaceutical product during safety evaluation period, and which does not necessarily need to have a causal relationship with the treatment.

The investigator (or subinvestigator) will assess AEs that occur in the subjects from the start of study drug administration to the end-of-study assessment and record the results in the CRF.

##### (1) Symptoms and diseases

The investigator (or subinvestigator) will assess whether any AE has occurred in the subjects based on the interview and physical examination.

##### (2) Objective findings

The investigator (or subinvestigator) will identify any clinically significant abnormal finding\* and handle it as an AE.

\* "Clinically significant abnormal findings" will be identified according to the following criteria.

- If a clinical sign or symptom is related to the abnormal findings.  
If these symptoms or signs are reported as AEs, the related abnormal laboratory findings will not be reported as separate AEs.
- If any internal or surgical treatment is given to the subject for the laboratory abnormality.
- If the study drug dosing regimen is changed due to the laboratory abnormality (e.g., dose change, or an interruption or discontinuation of the study drug).
- If the investigator (or subinvestigator) judges the abnormality as clinically significant for other reason(s).

(3) Assessments and criteria of AEs

1) Date of onset

The date of onset is defined as the date when symptoms are detected or the date when a laboratory test is performed for laboratory abnormalities. In this study, the onset time will also be recorded for all AEs occurring during hospitalization.

2) Severity

The severity of AEs will be classified as shown below.

- (1) Mild: The event does not interfere with activities of daily living.
- (2) Moderate: The event interferes to some extent with activities of daily living.
- (3) Severe: The event interferes significantly with activities of daily living.

3) Seriousness

The seriousness of AEs will be classified as shown below.

1. Not serious: AEs not meeting the criteria listed in 2.
2. Serious: A serious AE (SAE) meets any of the following, from a) to g).
  - a) Death
  - b) A case which may lead to death
  - c) A case which requires hospitalization in a hospital or clinic, or extension of a hospitalization period for treatment
  - d) Disability
  - e) A case which may lead to disability
  - f) A case of a serious disease, according to the cases listed in a) through e)
  - g) A congenital disease or abnormality in later generations

4) Relationship to the study drug

The investigator (or subinvestigator) will assess whether any "reasonable relationship" exists between an AE and the study drug. The assessment will include such factors as the natural course of complications or underlying diseases, combination therapies, risk factors other than the study drug, and the temporal relationship of the event onset to the study drug administration (e.g., recurrence of the event after reintroduction of the study drug, disappearance of the event after discontinuation of the study drug). An AE that is judged as "reasonably related" to the study drug is defined as an ADR.

1. Reasonably related
2. Not reasonably related

5) Outcome

The outcome of AEs will be graded on the following 6-point scale.

1. Recovered
2. Recovering
3. Not recovered
4. Recovered with sequelae

5. Death
6. Unknown

6) Date of outcome

The date of outcome will be defined according to the outcome, as shown below.

Recovered: The date on which a subject has recovered. If the date of recovery cannot be determined, the date of confirmation or judgment of recovery will be used.

Recovering: The date of confirmation or judgment of recovering

Not recovered: The date of confirmation or judgment of not recovered

[figure not shown]
Recovered with sequelae: The date of confirmation or judgment of recovered with sequelae

Death: The date of death. If the date of death cannot be determined, the date of confirmation or judgment of death will be used.

Unknown: If the date of outcome cannot be determined due to the subject's death from a cause other than the AE, the date of death will be used. For other cases, the date of confirmation or judgment will be used.

During hospitalization in this study, the time of outcome will also be determined according to the above criteria. If the time of outcome cannot be determined, the time of confirmation of the outcome will be used.

7) Follow-up

- Period (1) consists of 7 days starting from the day after last dose. During Period (1), AEs will be assessed.
- Period (2) consists of  $\geq 7$  days starting from the day after completion of the end-of-study assessment. During Period (2), AEs that occur during the assessment period (dosing period + [1]) will be followed up.
- The courses of AEs that are followed up during Period (2) will be recorded in the CRF.
- The date of outcome for AEs that are recovering or not recovered will be the date of the last observation in Period (2), which will be recorded in the CRF.

- ADRs that are recovering or not recovered at the end of Period (2) will be subsequently followed up in Period (3).
- After the end of the assessment period (Period [1]), if there is any proper reason to prematurely terminate the follow-up, the investigator (or subinvestigator) will record the reason in the CRF and terminate the follow-up.

(4) Items to be recorded in the CRF

If an AE is detected, the investigator (or subinvestigator) will record the following in the field for AEs in the CRF: AE term\*, date of onset, severity, seriousness, relationship to the study drug, details of treatment if given (e.g., drug[s], therapy[ies]), outcome, and date of outcome. If the investigator (or subinvestigator) judges that it is not necessary to follow up an AE whose outcome is other than recovered, recovered with sequelae, or death, he/she will record the reason. If the investigator (or subinvestigator) judges the relationship to the study drug as "not reasonably related," he/she will record the reason.

\* "AE terms" will be determined according to the following rules.

- In principle, the diagnosis will be used as an AE term.
- If the diagnosis is not definite, the symptom(s) will be used.
- If existing multiple symptoms can be expressed in one diagnosis, the diagnosis will be used.
- Surgical interventions will not be used as AEs. If any diagnosed disease or symptom requires surgical intervention, it will be used as an AE.

#### 9.2.5 Pharmacokinetic Assessments

(1) Volume and time points of blood sampling

The subjects' blood will be drawn at the time points shown in the table below to measure plasma drug concentrations. The investigator (or subinvestigator) will record the date and time of blood sampling in the CRF. The drug concentration measurement laboratory will measure the plasma drug concentrations.

If any other tests are scheduled at the same time point of blood sampling for plasma drug concentration measurement, blood will be drawn at the scheduled time point, and other tests will be performed before or after blood sampling. In principle, a 12-lead ECG and vital signs (except for body temperature) will be measured before blood sampling for plasma drug concentration or safety evaluation.

The acceptable time range for each blood sampling time point will be specified in a separate document.

Part 1 (single-dose study)	Part 2 (multiple-dose study)

• Day 1: Pre-dose, 15 and 30 minutes post-dose, and 1, 1.5, 2, 4, 6, 8, and 12 hours post-dose

	

• Day 1: Pre-dose, 15 and 30 minutes post-dose, and 1, 1.5, 2, 4, 6, 8, and 12 hours post-dose

• Day 2: 24 and 36 hours post-dose

• Day 3: 48 hours post-dose

	

• Day 2: Pre-dose (24 hours after dosing on Day 1)

• Day 3 to Day X -1*: Pre-dose

• Day X*: Pre-dose, 15 and 30 minutes post-dose, and 1, 1.5, 2, 4, 6, 8, and 12 hours post-dose

• Day X + 1*: 24 hours after dosing on Day X*

• Day X + 2*: 48 hours after dosing on Day X*

--	---

\*X = duration (in the case of a 5-day administration, X = 5)

## (2) Collecting, processing, and storage of specimens

Promptly after drawing roughly 5.5 mL of blood from the vein into a vacuum tube with heparin, gently invert the tube several times. The subsequent procedures should be performed on ice and completed within 120 minutes after blood sampling.

Transfer the blood into a tube with a stabilizer that has been supplied by the sponsor, and centrifuge the tube at 4°C, 1500 g for 10 minutes, so as to complete the centrifugation within 30 minutes after blood sampling. Accurately place the specified amount of plasma into a tube with the fixed amount of internal standard, stabilizer, and buffer that has been supplied by the sponsor and store at ≤-70°C. Additional details regarding the procedure are provided in a separate procedure.

Pack the main specimen and send it with a sufficient amount of dry ice to [REDACTED]  
[REDACTED] using a door-to-door delivery service. At the request of the sponsor, ship the reserve specimens, as well.

[REDACTED]  
[REDACTED]

### 9.2.6 Pharmacodynamic Assessments

Holter ECG data will be collected at the time points shown in the table below. The investigator (or subinvestigator) will record the conduct of the test in the CRF.

Each subject will wear the Holter monitor from at least 1 hour pre-dose to the completion of recording at 48 hours post-dose.

Additional details regarding the procedures are specified in a separate procedure.

Part 1  (single-dose study)

• Day 1: 45, 30, and 15 minutes pre-dose, 15 and 30 minutes post-dose, and 1, 1.5, 2, 4, 6, 8, and 12 hours post-dose

• Day 2: 24 and 36 hours post-dose

- Day 3: 48 hours post-dose

: For Cohorts S4, S5, and S6

### 9.3 Blood Sampling Volume

The total blood sampling volume per subject for each cohort of this study is about 114.7 mL in Cohorts S1, S2, and S4 to S7, about 205.8 mL in Cohorts S3-1 and S3-2, and up to about 259.6 mL in Cohorts M1 and M2.

#### 1) Cohorts S1, S2, and S4 to S7

Test using the specimen	Volume of specimen (mL)	Number of specimens	Subtotal (mL)
Infection/virus test	4	1	4
Hematology	2	4	8
Biochemistry	6	4	24
Coagulation test	1.8	4	7.2
Plasma drug concentration measurement	5.5	13	71.5
Total (mL)			114.7

#### 2) Cohorts S3-1 and S3-2

Test using the specimen	Volume of specimen (mL)	Number of specimens	Subtotal (mL)
Infection/virus test	4	1	4
Hematology	2	6	12
Biochemistry	6	6	36
Coagulation test	1.8	6	10.8
Plasma drug concentration measurement	5.5	26	143
Total (mL)			205.8

#### 3) Cohorts M1 and M2

Test using the specimen	Volume of specimen (mL)	5-day administration		9-day administration		14-day administration	
		Number of specimens	Subtotal (mL)	Number of specimens	Subtotal (mL)	Number of specimens	Subtotal (mL)
Infection/virus test	4	1	4	1	4	1	4
Hematology	2	5	10	6	12	7	14
Biochemistry	6	5	30	6	36	7	42
Coagulation test	1.8	5	9	6	10.8	7	12.6
Plasma drug concentration measurement	5.5	25	137.5	29	159.5	34	187
Total (mL)		190.5		222.3			259.6

## **10. Assessment Methods and Criteria**

### **10.1 Safety**

AEs and ADRs (see "9.2.4.6 Adverse Events" for details.)

### **10.2 Pharmacokinetic Measurements**

The plasma drug concentrations of unchanged edaravone, sulfate conjugate, and glucuronide conjugate will be measured, and the following PK parameters will be calculated using a non-compartmental analysis.

(1) Plasma drug concentrations

Unchanged edaravone, sulfate conjugate, and glucuronide conjugate

(2) PK parameters

$AUC_{0-\text{last}}$ ,  $AUC_{0-12\text{hr}}$ ,  $AUC_{0-24\text{hr}}$ ,  $AUC_{0-\infty}$ ,  $C_{\text{max}}$ ,  $C_{\text{trough}}$ ,  $t_{\text{max}}$ ,  $t_{1/2}$ ,  $\lambda_z$ , MRT\*, CL/F\*,  $V_z/F^*$ , and  $V_{\text{ss}}/F^*$  (\*: calculated for unchanged edaravone only)

The laboratory that measures drug concentrations will prepare a plan for the measurements by the time the measurements are started, and prepare a report after completion of the measurements.

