Appendix 3 Procedures for Cohort Transition

## Attachment

Attachment Administrative Structure

List of Abbreviations

Abbreviations	Descriptions of abbreviations
ALP	Alkaline phosphatase
ALT	Alanine aminotransferase
AST	Asparate aminotransferase
ALS	Amyotrophic lateral sclerosis
BA	Bioavailability
BMI	Body mass index
CK	Creatine kinase
EDC	Electronic data capture
GCP	Good clinical practice
γ-GTP	γ-glutamyltranspeptidase
HBs	Hepatitis B surface
HCV	Hepatitis C virus
HDL-C	Cholesterol, HDL (high-density lipoprotein)
HIV	Human immunodeficiency virus
LDH	Lactate dehydrogenase
LDL-C	Cholesterol, LDL (low-density lipoprotein)
MCH	Mean corpuscular hemoglobin
MCHC	Mean corpuscular hemoglobin concentration
MCV	Mean corpuscular volume
PK	Pharmacokinetic(s)
QTcF	Fridericia's correction of the QT interval

List of Abbreviations for PK Parameters

Abbreviations	Descriptions of abbreviations
AUC	Area under the plasma concentration-time curve
CL/F	Apparent total clearance
C max	Maximum plasma concentration
C trough	Minimum plasma concentration
λ z	Terminal elimination rate constant
MRT	Mean residence time
t 1/2	Terminal elimination half-life
t max	Time to reach the maximum plasma concentration
V ss/F	Apparent distribution volume at steady state
V z/F	Apparent distribution volume at the elimination phase

Definition of Term

Term	Definition
Study period	Period of time starting from the day of obtaining consent to the time of completion of the end-of-study assessment (For subjects who have entered into the follow-up period, to the time of completion or termination of follow-up.)

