Japanese healthy elderly subjects and healthy adult male subjects received multiple doses (0.5 mg/kg, twice daily for 2 days), and the PK and safety were evaluated. Following multiple doses of 30-minute IV infusion, the PK of the unchanged drug and the metabolites in plasma were similar for the elderly subjects and adult male subjects, and no particular changes were observed in the urinary excretion. No particular differences were found in safety between the elderly and adult male subjects. In addition, no clinically significant findings were observed.

The population PK analysis was performed using the PK data from the 5 clinical pharmacology studies of IV edaravone administration to healthy adult subjects in Japan and Europe. As a result, no particular changes were observed in the PK profiles between Japanese and Caucasian by race, sex, age, or body weight. Following IV edaravone infusion to ALS patients at the approved dose of 60 mg/60 min, the calculated  $C_{max}$  and  $AUC_{0-\infty}$  were 1,049 ng/mL and 1,374 ng•hr/mL, respectively.[1]

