#### 3.2 Exclusion Criteria

Subjects who meet any of the following criteria between screening and study drug administration will be excluded from the study.

- (1) Subjects with a current or previous history of cardiac, hepatic, renal, gastrointestinal, respiratory, psychiatric, nervous, hematopoietic, or endocrine diseases, and those whom the investigator (or subinvestigator) deems unsuitable for the study
- (2) History of drug or food allergy
- (3) History of alcohol or drug abuse or dependence
- (4) Body mass index (BMI) of  $<18.0$  or  $>30.0$ , or body weight of  $<50$  kg  
(BMI formula: body weight [kg]/height [m], rounded to one decimal place)
- (5) Positive test for any of the following at screening: Hepatitis B surface antigen, serological test for syphilis, hepatitis C virus antibody, or human immunodeficiency virus antigen/antibody
- (6) Any clinically significant 12-lead ECG abnormalities, or QTc interval  $\geq 450$  msec
- (7) Blood donation or sampling with a total volume of  $\geq 400$  mL within 12 weeks,  $\geq 200$  mL within 4 weeks, or  $\geq 800$  mL within a year before providing informed consent
- (8) Blood component donation or blood sampling within 2 weeks before providing informed consent
- (9) Subjects who have undergone any surgery known to affect the gastrointestinal absorption of drugs
- (10) Subjects who do not agree to use an effective method of contraception from initiation of the study drug administration to 14 days after completion (discontinuation) of study drug administration
- (11) Subjects who have previously received edaravone

- (12) Subjects who have participated in another clinical study and received a study drug within 12 weeks before providing informed consent
- (13) Use of any drug(s) other than the study drug within 7 days before initiation of study drug administration
- (14) Subjects judged by the investigator (or subinvestigator) to be unsuitable for the study for any other reason

[Rationales for setting]

- (1) To ensure the safety of subjects and to exclude unhealthy subjects.
- (2) To perform the study safely and ethically.
- (3) To perform the study safely and ethically.
- (4) To reduce PK variability due to BMI differences.
- (5) To perform the study safely and ethically.
- (6) To perform the study safely and ethically.

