##### (1) Part 1 (single-dose study)

A single oral dose of the study drug will be given to subjects under fasting conditions in the morning or 30 minutes after breakfast. In Cohort S3-2, subjects in Cohort S3-1 will be given the same study drug that is allocated in Cohort S3-1 in a single oral dose after at least a 4-day washout period. Doses of Cohort S2 and thereafter are tentative. Based on the PK data obtained up to 24 hours post-dose and the safety data obtained up to 48 hours post-dose of the previous cohort, the sponsor and a medical expert will examine and determine the dose with the agreement of the investigator, such that the exposure of the minimum toxic dose (10,226 ng/mL for  $C_{max}$  and 1,226 ng•hr/mL for  $AUC_{0-24hr}$  in a free base form) is not exceeded. However, the highest dose in Part 1 shall not exceed 7,200 mg. The common ratio between the dose and the estimated mean  $C_{max}$  and  $AUC_{0-24hr}$  should be  $\leq 5$  between successive cohorts.

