**(2) Part 2 (multiple-dose study)**

A once-daily oral dose of the study drug will be given to subjects 30 minutes before breakfast. For twice-daily administration, an oral dose of the study drug will be given to subjects 30 minutes before breakfast and before bedtime (12 hours after the dose

before breakfast). (On Day 1 and Day X [day of the last dose], an oral dose of the study drug will be administered 30 minutes before breakfast only.) If effects of diet are predicted by oral administration 30 minutes before breakfast from the results of pharmacokinetics obtained in cohorts S3-1, S3-2 and M1, it is possible to change cohort M2 to oral administration 1 hour or 90 minutes before breakfast, or not to take breakfast after fasting administration only on the administration day.

The dose and duration for Cohorts M1 and M2, and the frequency of administration for Cohort M2 are tentative. Based on the PK and safety data collected in Part 1 and Cohort M1, the sponsor and the medical expert will examine and determine the actual value with the agreement of the investigator. The dose in Cohort M2 should be  $\leq 2/3$  of the highest dose in Part 1. The common ratio between the dose and the estimated mean  $C_{max}$  and  $AUC_{0-24hr}$  should be  $\leq 5$  between successive cohorts.

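### Vss/F is to come from non-compartmental analysis of oral data alone, which overstates it by the factor 1 + MAT/MRT(iv); the effect is confined to one descriptive endpoint

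*Protocol*

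**What the plan says.** Section 10.2 lists MRT, CL/F, Vz/F and Vss/F, says that "the following PK parameters will be calculated using a non-compartmental analysis", and marks these four as "calculated for unchanged edaravone only". Section 5.4.2 and Summary 6.2 list the same endpoints. The List of Abbreviations for PK Parameters defines Vss/F as "Apparent distribution volume at steady state" and MRT as "Mean residence time", without distinguishing oral from IV.

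All dosing is oral. For Part 1, section 8.3.1 says: "A single oral dose of the study drug will be given to subjects under fasting conditions in the morning or 30 minutes after breakfast". For Part 2 it says: "A once-daily oral dose of the study drug will be given to subjects 30 minutes before breakfast", with an optional twice-daily oral regimen in M2. There is no IV arm or IV period. Exclusion criterion (11) removes "Subjects who have previously received edaravone", so no subject brings earlier IV data of his own.

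IV results appear as background in 1.3.2, where Cmax and AUC0-∞ after 60 mg over 60 minutes "were 1,049 ng/mL and 1,374 ng•hr/mL, respectively", and in the dose and bioavailability rationale of 8.3.1. The protocol mentions neither a mean absorption time nor a correction to MRT, and it does not say that IV data will supply MRT.

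**The concern.** The relation Vss = CL × MRT holds when MRT describes disposition only, as after an IV bolus. An oral profile also contains the time spent in absorption. Its moments give only the sum of the two times, so oral data alone cannot separate them. The plan names both the parameter and the method, and this trial's data cannot yield that parameter by that method.

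The error also need not be constant across cohorts, because the design may vary absorption. Under 7.1 the comparator is a solution in S1 and a suspension afterwards, and S4 adds xanthan gum. S3-2 is dosed after a high-fat breakfast (8.6.3). Differences in dissolution are part of a secondary objective (section 2). If absorption time differs between these conditions, reported Vss/F will differ too, and a reader of the tables could take an absorption effect for a change in distribution.

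**Working it through.** The protocol gives no value or formula for Vss/F, so there is no stated figure to reproduce. The check uses the moment identity, assuming linear kinetics.

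**Identity.** MRT(oral) = MRT(iv) + MAT. True Vss/F = CL/F × MRT(iv). The non-compartmental value from oral data is CL/F × MRT(oral). Reported/true = 1 + MAT/MRT(iv), which exceeds 1 whenever MAT is above zero.

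**One-compartment illustration from the protocol's exposures.**

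- IV inputs (1.3.2): 60 mg over 1 h, Cmax 1,049 ng/mL, AUC0-∞ 1,374 ng·hr/mL. For a 1-h infusion Cmax/AUC = 1 − exp(−k), so k = −ln(1 − 1,049/1,374) = 1.44/h and MRT(iv) = 1/k = 0.69 h.
- Oral inputs (8.3.1, projected for 60 mg): Cmax 93 ng/mL, AUC0-24hr 202 ng·hr/mL. AUC/Cmax = 202/93 = 2.17 h = exp(k·tmax)/k, so tmax = ln(1.44 × 2.17)/1.44 = 0.79 h.
- Solving ln(ka/k)/(ka − k) = 0.79 gives ka = 1.10/h and MAT = 1/1.10 = 0.91 h.
- MRT(oral) = 0.69 + 0.91 = 1.60 h. Overstatement = 1.60/0.69 = 2.3-fold.

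In this reading ka is below k, so the terminal slope is ka. Vz/F, computed as CL/F divided by the terminal slope, is then inflated by 1.44/1.10 = 1.31-fold. Reported Vss/F would be 1.60 × CL/F against a reported Vz/F of 0.91 × CL/F, an ordering that true volumes cannot have.

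**Range of 1 + MAT/MRT(iv) over assumed values.**

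| MRT(iv), h | MAT 0.1 h | 0.25 h | 0.5 h | 1 h | 2 h |
|---|---|---|---|---|---|
| 0.7 | 1.14 | 1.36 | 1.71 | 2.43 | 3.86 |
| 1.5 | 1.07 | 1.17 | 1.33 | 1.67 | 2.33 |
| 3 | 1.03 | 1.08 | 1.17 | 1.33 | 1.67 |
| 6 | 1.02 | 1.04 | 1.08 | 1.17 | 1.33 |

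**Two-compartment check.** Noise-free oral profiles with assumed parameters (MRT(iv) 2.0, 2.5 and 5.6 h; F = 0.12) were evaluated at the Part 1 sampling times, with linear-up/log-down AUC and AUMC. The ratio of non-compartmental to true Vss/F was:

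- MAT 0.5 h: 1.09 to 1.31
- MAT 1 h: 1.18 to 1.55
- MAT 2 h: 1.37 to 2.06

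These lie close to the identity. At MAT 0.1 to 0.25 h the ratio was 1.07 to 1.23, above the 1.02 to 1.12 of the identity, because sparse early sampling adds integration error.

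**Could cohorts differ with no change in distribution?** With true Vss/F held constant and MAT moved from 0.25 to 2 h:

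- MRT(iv) 2.0 h: 880 to 1,493 L (+70%)
- MRT(iv) 5.6 h: 2,149 to 2,736 L (+27%)

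Both depend on the assumed change in MAT.

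**The case against.** **The formula is not in the protocol.** Section 10.2 names the parameter and the method but not CL/F × MRT(oral), and 13.1 leaves detailed procedures to a separate SAP, which could import MRT(iv) from the sponsor's IV studies. That possibility stands as a way to repair the plan. It does not rescue the text: the stated method applied to this trial's data cannot identify the stated quantity, and the protocol does not foresee external data for it.

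**Nothing turns on Vss/F.** This stands in full. Cohort transition (8.4) uses safety results, plasma concentrations, Cmax and AUC. In 13.4, dose proportionality and the food effect use Cmax and AUC, and the Part 2 analyses use AUC and Ctrough. A reader might infer that dose decisions or planned comparisons are compromised. The documents do not support that.

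**The 2.3-fold figure is fragile.** This also stands. It assumes one compartment, with an implied half-life of ln 2/1.44 = 0.48 h, in a study that samples to 48 h. It combines model-based IV values for ALS patients with pre-trial oral projections, and AUC0-∞ with AUC0-24hr. The two sets imply a bioavailability of 202/1,374 = 14.7%, against the 12% stated in 8.3.1. It is an illustration and should not be read as an estimate of the bias. With slow disposition and fast absorption the bias is trivial.

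**A false dose trend is conditional.** A reader might infer that Vss/F will rise with dose. That needs MAT to change with dose, and the protocol gives no MAT data.

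**Vz/F is not a clean substitute.** Correct where absorption is rate-limiting, as the 1.31-fold figure shows. Deleting Vss/F and treating Vz/F as free of the problem would be inconsistent.

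**Conclusion.** The point holds as an error in how one descriptive endpoint is fixed. Under linear kinetics, following 10.2 gives CL/F × (MRT(iv) + MAT), which is always larger than the volume that the abbreviation list defines. The documents do not determine the size: the one-compartment illustration gives about 2.3-fold, and the assumed ranges run from near 1 to nearly 4-fold. Differences between cohorts that reflect only absorption are possible but not established. The consequence is a mislabelled, upward-biased value in the descriptive PK tables. Safety, dose selection and the planned comparisons are unaffected. The change is still worth making, because a published steady-state volume may be reused by readers who do not see how it was obtained.

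**What to change.** Choose one:

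- Delete Vss/F from 5.4.2, 10.2 and Summary 6.2, and from the abbreviation list. This loses one descriptive parameter.
- Keep Vss/F, but state that it is CL/F × MRT(iv) and name the external IV source of MRT(iv). The IV population PK report (reference [1]) is a candidate, but it is not available here, so whether it yields MRT(iv) must be confirmed. If MRT comes from infusion profiles, half the infusion time must first be subtracted (60/2 = 30 minutes for a 60-minute infusion). The cost is reliance on data from other subjects.

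In either case, label the reported MRT as oral MRT including absorption time, and add a footnote that Vz/F is also inflated where absorption is rate-limiting. The edit is a line or two in the protocol, with the matching derivation rule in the SAP. Section 13.5 already allows changes to the analysis plan before data lock, with the reason recorded.
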